### **6.3.1 Baseline Data**

Baseline and demographic characteristics will be summarized by standard descriptive statistics (including mean and standard deviation for continuous variables such as age and standard percentages for categorical variables such as gender).

### **6.3.2 Analysis of Primary Outcome of Interest**

The primary outcomes of interest will be analyzed based on the data distribution with a goal of determining the averages and the standard deviations within the dataset.

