Any upper airway procedure we perform begins with direct laryngoscopy and the exposure of the glottic airway with a laryngoscope. With the exposed view of the vocal cords/glottic opening, the exchange step of endotracheal intubation or placement of the HFJV cannula takes a few seconds. The surgical and anesthesia staff assigned to these cases are familiar with the exchange from one mode of oxygenation to another since this is commonly performed for these cases. After performing a portion or the entire case with HFJV, the team generally elects to intubate the patient for the final steps of the surgical case or for emergence from anesthesia. In cases where HVNI is used, the surgeon and anesthesiologist team will then decide if the patient will continue to receive oxygenation through the nasal cannula, get mask ventilated, or get intubated. Investigators for this study do not anticipate any additional risks to the patient or significant additional time needed to complete these procedures during this study, even in the cases where use of Hi-VNI alone is insufficient.

All surgical aspects of the case will be captured using video recording, which is standard for all upper airway surgeries at our institution performed with use of an endoscope or a microscope. A review of the video recordings for the cases included in the study will help us better understand how tubeless surgical space impacts the length of the case (from the time laryngeal exposure is visualized to the end of the case) and to visually document the airway pathology treated with Hi-VNI. The duration of induction, the procedure itself and the emergence from anesthesia will be measured. Post-operative recovery of each participant will be assessed from the standpoint of any airway related complications, prolonged drowsiness or other complications pertinent to this study. Additional information about the ease of Hi-VNI use and any difficulties encountered during the surgical case will be recorded. Patients will also be asked to rate the comfort of the procedure including sore throat and irritation, which is anticipated to be less with the HVNI technique.

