### Schedule of events:

### 3.4 Study Endpoints

#### 3.4.1 Primary Study Endpoint

The primary endpoint for this study will be case completion rate without alternative mode of oxygenation. In other words, for each case, the ability to complete the surgical procedure with use of only Hi-VNI device for oxygenation will be assessed.

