### **5.4 Subject Withdrawal**

All study subjects may withdraw from the study at any time without impact to their care. They may also be discontinued from the study at the discretion of the PI and co-Is if it is determined that they are not good candidates for Hi-VNI use immediately prior to surgical procedure or during the surgical procedure. This decision will be made based on a joint discussion between the airway surgeon and the anesthesiologist.

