#### **5.4.1 Data Collection and Follow-up for Withdrawn Subjects**

Subjects who choose to withdraw from the study or will be withdrawn from the study at the discretion of the PI or co-I will not require any additional follow-up data collection for this study.

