Using a normal end-tidal CO2 value of 37.5 mmHg and adding this value to the limits of the range of change in TcpCO2 listed above will give us a range of the values for TcpCO2 at the end of the procedure assuming the average duration of the procedure is  $22.5 \pm 4.5$  min. This range of the TcpCO2 at the end of the procedure would be [57.75; 67.88]. Our cutoff of TcpCO2 minus the baseline gradient between TcpCO2 and end-tidal CO2  $> 55$  mmHg is when the mode of oxygenation will be changed from Hi-VNI to an alternate method (endotracheal intubation or HFJV). The baseline gradient will be measured as the TcpCO2 minus the end-tidal CO2 during routine pre-oxygenation with a facemask. Based on the normal distribution assumption, one can deduce that only procedures with the duration one standard deviation away from the mean duration value of 22.5 min will not reach this level of TcpCO2. In other words, approximately 16% of patients will not require alternate means of ventilation (population which falls to the left of the line through a value of (22.5-4.5) on the normal distribution curve or 15.85%). Based on the author's prior experience and operative volume, there are 2-3 elective cases per week performed by the PIs that may qualify based on the inclusion/exclusion criteria to be included in the study. If 3 cases per week is used will equal to 144 qualified cases per year. For the confidence interval of 95% and the margin of error of 5% with the rate of 16%, the calculated sample size will equal to 86 individuals who might have a good chance of having their procedure completed with Hi-VNI without a need to switch to alternate mode of oxygenation. To account for the fact that some patients may not consent to be in the study or may require alternate means of oxygenation after Hi-VNI is used for other reasons, we added 14 patients to the sample size. This would lead to an estimated sample size of 100 individuals.

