## **6.2 Statistical Methods**

Descriptive statistics will be used to characterize the data distribution with normally distributed data presented as means and standard deviation, otherwise median and interquartile range will be used. Proportions will be presented in numbers and percentages. All data analyses will be performed using a statistical tool (SPSS, version 15.0, SPSS). Mann-Whitney U test or Student's t-test and Kruskal-Wallis or ANOVA test will be used depending on the data distribution and the number of variables. All statistical analyses will use a  $p < 0.05$  as statistically significant. Any additional statistical analyses will be determined during secondary data analysis with help from a statistician.

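### No rule keeps cases that the investigators discontinue during surgery in the completion-rate denominator as not completed, and the 95% CI behind the sample size is missing from the analysis plan

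*Combined protocol and SAP*

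**What the plan says.** - **Endpoint (3.4.1).** The primary endpoint is the case completion rate. For each case, "the ability to complete the surgical procedure with use of only Hi-VNI device for oxygenation will be assessed".
- **Removal before Hi-VNI (3.3, 10.1).** A patient who cannot be mask ventilated at induction leaves the study. This happens before Hi-VNI is started.
- **Removal during surgery (5.4).** The investigators may discontinue subjects whom they judge to be "not good candidates for Hi-VNI use immediately prior to surgical procedure or during the surgical procedure". Under 5.4.1, withdrawn subjects "will not require any additional follow-up data collection for this study".
- **Sample size (6.1).** The figure of 86 is derived as follows: "For the confidence interval of 95% and the margin of error of 5% with the rate of 16" per cent. The plan then goes to 100 because some patients may decline consent or "may require alternate means of oxygenation after Hi-VNI is used for other reasons, we added 14 patients to the sample size".
- **Analysis (6.2, 6.3.2).** Section 6.2 states: "Proportions will be presented in numbers and percentages". Section 6.3.2, the only section on analysis of the primary outcome, sets out to analyse it "with a goal of determining the averages and the standard deviations within the dataset". The only mention of a confidence interval for the rate is in 6.1.

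**The concern.** A patient who does badly on Hi-VNI during surgery can be described in two ways. Under 3.4.1 the case is a non-completion. Under 5.4 the patient may be judged a poor candidate and discontinued. The first description keeps the case in the denominator. The plan does not say what the second does. The decision is taken during surgery, in a single-arm study without blinding, by investigators who can see how the case is going.

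Section 6.1 adds to the doubt. Some patients who need another mode of oxygenation after Hi-VNI are grouped with non-consenters, as losses to be made up by recruiting more. A non-consenter never enters the study. A patient who needed another mode after Hi-VNI has been treated and has failed the primary endpoint, so no replacement is needed.

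The completion rate is the study's main result. If treated failures can leave its denominator, the rate can move in one direction only, and a reader could not tell by how much. The secondary matter is reporting. The study is sized for the precision of this proportion, yet the analysis sections plan no statement of that precision.

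**Working it through.** **Step 1: reproduce the sample size in 6.1.** The inputs, all from 6.1, are a rate of 16%, 95% confidence, a margin of 5 points and 144 qualifying cases per year.

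- Without correction: n0 = 1.96² × 0.16 × 0.84 / 0.05² = 206.5.
- With finite-population correction: 206.5 / (1 + 205.5/144) = 85.1, rounded up to 86. This matches the stated figure.
- Adding 14 gives 100.

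The correction is not named in 6.1, but the 144 cases yield 86 and the uncorrected formula does not. The statistical basis for the size is therefore a 95% CI for one proportion.

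**Step 2: the half-width that this implies at 16%.**

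- n = 100, uncorrected: 1.96 × √(0.16 × 0.84/100) = 7.2 points.
- n = 100, corrected: 7.2 × √(44/143) = 4.0 points.
- n = 86: 7.7 points uncorrected, 4.9 corrected.

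The exact interval for 16/100 is 9.4% to 24.7%, that is 6.6 points below and 8.7 above. The 5-point margin is met only with the correction.

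**Step 3: the effect of dropping failures.** If x of 100 cases complete and d failures are removed, the rate becomes x/(100 − d), which is the true rate multiplied by 100/(100 − d). With x = 16 (exact Clopper-Pearson intervals):

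| Failures dropped | Rate | Exact 95% CI | Factor |
|---|---|---|---|
| 0 | 16/100 = 16.0% | 9.4% to 24.7% | 1.00 |
| 5 | 16/95 = 16.8% | 9.9% to 25.9% | 1.05 |
| 10 | 16/90 = 17.8% | 10.5% to 27.3% | 1.11 |
| 14 | 16/86 = 18.6% | 11.0% to 28.4% | 1.16 |
| 20 | 16/80 = 20.0% | 11.9% to 30.4% | 1.25 |

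The counts 5, 10 and 20 are assumptions. The row for 14 is an upper bound for the allowance in 6.1, since that allowance also covers non-consent. The factor does not depend on the true rate, so the shift in points grows with it. At an assumed 50%, dropping 10 failures gives 50/90 = 55.6% and dropping 20 gives 50/80 = 62.5%.

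**Step 4: what 6.3.2 would report.** For a yes/no outcome at 16% the average is the proportion itself and the standard deviation is √(0.16 × 0.84) = 0.37. That number is fixed by the proportion and says nothing about precision.

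**The case against.** The strongest reply is that the natural reading already keeps failures in. The endpoint is assessed for each case. The switches required for low saturation, high CO2, arrhythmia or hypotension, cautery or laser (3.3, 10.1) are nowhere called withdrawals, whereas failed mask ventilation is expressly removed. Section 3.1 looks for suitable scenarios among cases completed without adjuncts, which makes sense only if switched cases stay in the data. All of this stands, and it confines the gap to discretionary discontinuation under 5.4.

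A reader might infer more than the documents support:

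- **That data on discontinued subjects are thrown away.** Section 5.4.1 waives only further follow-up, no subject has long-term follow-up (4.1, 5.2), and the completion outcome is known in the operating room. The gap is a missing counting rule.
- **That the 14 extra patients are an allowance for failures in general.** At 16%, about 84 of 100 patients would switch. The allowance is limited to other reasons and mixed with non-consent. It suggests how such cases are viewed but does not show that they will be excluded.
- **That the completion rate would not be reported as a proportion.** Section 6.2 provides number and percentage, from which a reader could compute an interval. What is missing is a planned interval.
- **That the endpoint has no end time.** Section 3.3 leaves open whether a Hi-VNI patient will "get mask ventilated, or get intubated" late in the case. But 3.4.1 already limits the endpoint to the surgical procedure, and 3.4.2 separates the end of the case from emergence.

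It can also be said that this is a pilot with no decision threshold on the rate, and that 6.1 cites caseload and a one-year limit as well as precision. That lowers the stakes. It does not remove the need for a fixed denominator, because a single-arm descriptive study has little else to support its main figure.

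**Conclusion.** The point holds as a modest correction that should be made. The omission is certain: no section states whether a subject discontinued by the investigators after Hi-VNI has started counts as not completed. That such cases will be dropped is a possibility the text allows, not something it states.

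If it happened, the rate would be multiplied by 100/(100 − d). At 16% and with 5 to 20 failures dropped (assumed), the rise is 0.8 to 4.0 points. That lies inside the exact interval for 16/100 but is always upward. The rise in points would be larger at a higher true rate.

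The interval is the secondary point. Averages and standard deviations do not suit a binary endpoint, and the 95% CI used for sizing should be carried into the analysis.

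**What to change.** In 6.3.2, add:

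> Completion rate = cases in which surgery was completed with Hi-VNI as the only oxygenation method, divided by all patients in whom Hi-VNI was started, with an exact (Clopper-Pearson) 95% CI. Any patient switched to another mode, aborted, or discontinued by the investigators after Hi-VNI start and before the end of surgery stays in the denominator as not completed, with reasons tabulated. Patients excluded before Hi-VNI start, including failed mask ventilation, are reported as a count.

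Planned-adjunct cases (3.2) stay in this denominator. A breakdown by primary or adjunct use may be shown in addition. Keep averages and standard deviations for the continuous measures.

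In 5.4.1, add that for subjects discontinued by the investigators after Hi-VNI start, the completion outcome and the reason are retained.

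The cost is a few sentences. Both data items are known in the operating room, and no clinical rule changes. There are two downsides. The reported rate may be slightly lower. The stated precision will also look less favourable: at 16/100 the exact interval extends about 7 points below and 9 above, against the 5-point margin in 6.1, which is met only with the finite-population correction at 144 cases. The plan should say so.

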## **7 Safety and Adverse Events**

### **7.1 Definitions**

#### **7.1.1 Adverse Event/Adverse Device Effect**

An adverse event (AE)/adverse device effect (ADE) is any symptom, sign, illness or experience that develops or worsens in severity during the course of the study. Intercurrent illnesses or injuries should be regarded as adverse events. Abnormal results of diagnostic procedures are considered to be adverse events if the abnormality:

- results in study withdrawal
- is associated with a serious adverse event
- is associated with clinical signs or symptoms
- leads to additional treatment or to further diagnostic tests
- is considered by the investigator to be of clinical significance

### **7.2 Serious Adverse Event**

Adverse events are classified as serious or non-serious. A serious AE is any AE that is:

- fatal
- life-threatening
- requires or prolongs hospital stay
- results in persistent or significant disability or incapacity
- required intervention to prevent permanent impairment or damage
- a congenital anomaly or birth defect
- an important medical event

Important medical events are those that may not be immediately life threatening, but are clearly of major clinical significance. They may jeopardize the subject, and may require intervention to prevent one of the other serious outcomes noted above. For example, drug overdose or abuse, a seizure that did not result in in-patient hospitalization, or intensive treatment of bronchospasm in an emergency department would typically be considered serious.

All adverse events that do not meet any of the criteria for serious should be regarded as non-serious adverse events.

## **Unanticipated Adverse Device Effect (UADE)**

A UADE is any serious adverse effect on health or safety, or any life-threatening problem or death caused by, or associated with, a device, if that effect, problem, or death was not previously identified in nature, severity, or degree of incidence in the investigational plan or application, or any other unanticipated serious problem associated with a device that relates to the rights, safety, or welfare of subjects.

### **7.3 Recording of Adverse Events**

All adverse events occurring during the study period will be recorded. The clinical course of each event will be followed until resolution, stabilization, or until it has been determined that the study intervention or participation is not the cause. Serious adverse events that are still ongoing at the end of the study period will be followed up to determine the final outcome. Any serious adverse event that occurs after the study period and is considered to be possibly related to the study intervention or study participation will be recorded and reported.

### **7.4 Relationship of AE to Study**

The PI will determine the relationship of each adverse event to the study procedures. Relationship will be classified as definitely related, probably related, possibly related, or not related.

### **7.5 Reporting of Adverse Events and Unanticipated Problems**

The Investigator will promptly notify the Penn IRB of all on-site unanticipated, Adverse Events that are related to the research activity. Other unanticipated problems related to the research involving risk to subjects or others will also be reported promptly. Written reports will be filed using the HS-ERA and in accordance with the Penn IRB timeline of 10 working days.

#### **7.5.1 Follow-up Report**

If an AE has not resolved at the time of the initial report and new information arises that changes the investigator's assessment of the event, a follow-up report including all relevant new or reassessed information (e.g., concomitant medication, medical history) should be submitted to the IRB. The investigator is responsible for ensuring that all SAEs are followed until either resolved or stable.

#### **7.5.2 Data and Safety Monitoring Plan**

The PI and the co-Is for this study will be responsible for data and safety monitoring. No formal data safety monitoring committee will be designated for this study since the PI and the sub-Is will closely monitor data safety for this study.

## **8 Study Administration, Data Handling and Record Keeping**

### **8.1 Confidentiality**

Information about study subjects will be kept confidential and managed according to the requirements of the Health Insurance Portability and Accountability Act of 1996 (HIPAA). Those regulations require a signed subject authorization informing the subject of the following:

- What protected health information (PHI) will be collected
- Who will have access to that information and why
- Who will use or disclose that information
- The rights of a research subject to revoke their authorization for use of their PHI.

In the event that a subject revokes authorization to collect or use PHI, the investigator, by regulation, retains the ability to use all information collected prior to the revocation of subject authorization.

### **8.2 Data Collection and Management**

The primary source of data collection for this study will be the current electronic medical record (EMR) system used at the University of Pennsylvania Health System (UPHS) and intra-operative/post-operative findings and observations recorded by the study personnel. During the selection of potential study participants, the electronic medical records will be reviewed by the PI/Co-Is, who will confirm eligibility based on the inclusion and exclusion criteria. If the case meets eligibility, the research team will proceed with informed consent either prior to or on the day of the scheduled surgical procedure.

Qualified patients will be assigned a unique study identification number (UID). Data will be abstracted electronically in a comma separated variable format for a statistical software package. The databases will be maintained on an institutionally secured and managed network drive. Only members of this research study team will have access to the data. Birth date will only be used to calculate an exact age in years and months. Upon completion of data collection, the age will replace the birth date. A master data sheet will include the relevant personal health information (PHI) for the study with the matching UID numbers. A separate data sheet used for statistical analyses will have only the UID numbers with de-identified information.

### **8.3 Records Retention**

The electronic data as well as paper and digital records collected during this study will be destroyed within five years following publishing.

## **9 Study Monitoring, Auditing, and Inspecting**

### **9.1 Study Monitoring Plan**

The study PI and sub-Is will be responsible for ensuring the ongoing quality and integrity of the research study.

CONFIDENTIAL

This material is the property of the University of Pennsylvania.

## **9.2 Auditing and Inspecting**

The investigator will permit study-related monitoring, audits, and inspections by the IRB, government regulatory bodies, and University compliance and quality assurance groups of all study-related documents. The investigator will ensure the capability for inspections of applicable study-related facilities.

Participation as an investigator in this study implies acceptance of potential inspection by government regulatory authorities and applicable University compliance and quality assurance offices.

## **10 Ethical Considerations**

All study team members have experience/training in clinical research and have completed their CITI human subjects training. All study team members will be asked to document their role on the study delegation log. Ongoing training will take place as needed. The investigators will maintain open communication with study staff and IRB, and will submit protocol changes to IRB for approval prior to implementing them.

### **10.1 Risks**

All subjects included in this study will be informed about potential risks associated with the use of the Hi-VNI device during surgery based on the previously published studies and the safety information reported by the Hi-VNI device manufacturer. These risks include nasal discomfort and/or rhinorrhea. To our knowledge, no other risks have been previously directly linked to Hi-VNI use. These side effects of Hi-VNI use could be related to dry nasal mucosa after use of high-flow nasal insufflation, and will prescribe nasal saline sprays and recommend Tylenol or other mild over the counter analgesics in cases when patients report symptoms of nasal pain and/or rhinorrhea.

To minimize the risk of inadequate oxygenation and other complications, careful continuous monitoring will be maintained throughout the case. All patients will receive preoxygenation with a bag-mask to ensure that mask ventilation can be performed successfully during the case if needed and to determine the baseline gradient between end-tidal CO2 and TcpCO2. If mask ventilation during the induction phase is unsuccessful, the anesthesia team will intubate the patient or HFJV will be initiated after exposure of the glottis by the airway surgeon, and the patient will be withdrawn from the study.

The Hi-VNI device will be used during the surgical procedure with continuous monitoring by anesthesia team. If at any point the SpO2 drops below 90% or the value of TcpCO2 minus the baseline gradient rises above 55 mmHg, the airway surgeon and the anesthesiologist will stop the procedure and will switch to an alternate means of oxygenation immediately by placing an HFJV cannula or a small sized endotracheal tube through the laryngoscope into the glottis/trachea (a step performed in the beginning of the case if HFJV or endotracheal intubation are selected as primary methods of oxygenation during the case). Continuous monitoring in the OR will help us avoid TcpCO2 minus the baseline gradient levels above 55 mmHg (levels of TcpCO2 not previously correlated clinically with PaCO2). As soon as this threshold value is reached, the surgeon will place an endotracheal tube through the

laryngoscope. A total of 5 breaths will be administered via the endotracheal tube to determine the ETCO2 reading. If the ETCO2 reading is above 60 mmHg, the patient will be ventilated via the endotracheal tube. In other words, continuous monitoring will ensure that clinically significant hypoxia or hypercarbia (defined as SpO2 level below 90% or ETCO2 levels above 60 mmHg) that could eventually lead to adverse events if not promptly corrected will always be avoided by immediate switch to alternate means of oxygenation. HFJV equipment, a small sized endotracheal tube, and all standard operating room airway and resuscitation equipment will be available as is the current standard during each case to allow for safe use of Hi-VNI and to prepare for the cases in which alternate means of oxygenation may be required.

All precautions will be taken to prevent vital sign changes that affect the accuracy of TcpCO2 measurements including changes in blood pressure, abnormal heart rhythm or body temperature changes. Warming blankets will be used to avoid hypothermia. If a patient develops a transient arrhythmia or hypotension requiring vasopressor administration during the procedure, which can cause erroneous SpO2 and inaccurate TcpCO2, the patient will be intubated and the procedure will be completed with oxygenation/ventilation via the endotracheal tube. If the procedure cannot be performed with the endotracheal tube in place, the procedure will be aborted. If the arrhythmia persists, or if the nature of the arrhythmia is considered to warrant procedure termination, the procedure will be aborted. Additionally, if use of Hi-VNI support extends beyond 20 minutes, a blood sample will be drawn to evaluate CO2 level (PaCO2 or PvCO2). If the blood sample collection cannot be done, the patient will be intubated and ETCO2 will be measured.

If at any point during the procedure, a bleeding is encountered that requires cautery, the team will switch to an endotracheal tube to prevent aspiration of blood into the airway and to allow for appropriate hemostasis with use of cautery. If at any point during the procedure, it will become evident that the laser use is necessary, the team will switch to an alternate means of oxygenation. Standard practices currently in place to avoid airway fire will be used if the case demands use of electrocautery or laser. These practices will be implemented immediately once it becomes evident that either laser or electrocautery will be used. If laser or electrocautery will be used to control the bleeding during the case, following an endotracheal intubation, appropriate washout of residual oxygen will take place per routine protocol, and the laser or cautery will not be used until FiO2 levels reach the values below 21%. All standard fire precautions will be used and the oropharynx will be suctioned to remove any potential residual oxygen excess. All cases will be screened prior to enrollment into the study to avoid inclusion of the cases with high risk of large-volume bleeding requiring cautery or with a need for laser use during the procedure.

Any upper airway procedure we perform begins with direct laryngoscopy and the exposure of the glottic airway with a laryngoscope. With the exposed view of the vocal cords/glottic opening, the exchange step of endotracheal intubation or placement of the HFJV cannula takes a few seconds. The surgical and anesthesia staff assigned to these cases are familiar with the exchange from one mode of oxygenation to another since this is commonly performed for these cases. After performing a portion or the entire case with HFJV, the team then elect to intubate the patient for the final steps of the surgical case or for emergence from

anesthesia. In cases where HVNI is used the surgeon and anesthesiologist team will then decide if the patient will continue to receive oxygenation through the nasal cannula, get mask ventilated or get intubated. Investigators for this study do not anticipate any additional risks to the patient or significant additional time needed to complete these procedures during this study, even in the cases where use of Hi-VNI alone is insufficient.

Patients who are not candidates for Hi-VNI use will be excluded from this study. These patients include those with underlying medical conditions in which brief periods of hypoxemia or hypercarbia are not well-tolerated, such as pregnant patients, patients with coronary artery disease or carotid/vertebral artery stenosis, patients with severe heart failure or implanted ICD, patients with extremely low or extremely high BMI or patients with baseline hypoxia and oxygen requirement at home. Additionally, patients in whom use of high-flow oxygenation is contraindicated, such as patients with increased intracranial pressure or history of skull base surgery, will be excluded. Patients at high risk for aspiration and patients scheduled for emergent or urgent interventions will also be excluded.

